# 3) Objectives:

The purpose of this study is to implement an additional module related to COVID-19 to our pilot peer-driven intervention that seeks to address a cluster of health issues that have been shown to impact Latino immigrant communities. These health problems include Substance Abuse, Violence exposure, HIV/AIDS, and Mental Health (SAVAME). These conditions represent a syndemic because they act synergistically, and stem from multiple, common social and environmental determinants. The Cultivating Resilient and Strong Opinion Leaders (CRiSOL) intervention aims to reduce the impact of the SAVAME syndemic and COVID-19 among Latino immigrants in Philadelphia by integrating a community resilience and opinion leader framework.

The specific aims of the pilot study are:

- 1. To adapt and integrate two interventions previously implemented by our community partners in order to develop a new intervention to reduce the impact of the SAVAME syndemic among Latino immigrants in Philadelphia, with emphasis on changing social norms, promoting utilization of SAVAME-related health, behavioral, and social services, and promotion of individual and community resilience.
- 2. To recruit and train a small sample of peer leaders and implement the Creating Resilient and Strong Opinion Leaders (CRiSOL) pilot intervention in Philadelphia communities where Latino communities concentrate.
- 3. To test the pilot intervention using a comprehensive evaluation framework to generate feasibility, acceptability, and pilot efficacy data that will inform a future R01 application proposing an effectiveness trial of this intervention.
- 4. Include an additional 16-hour module related to COVID-19 to our previous implemented pilot.

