#### Community contacts:

As interventionists and data collectors, POLs will interact (i.e. face to face, social media, by phone) with community contacts within their own social networks during POL outreach. They will document the reach of the intervention using iPads provided by our project and equipped with the Qualtrics survey software offline application or using a link on their phones.

Every time they interact with a community contact as part of the CRiSOL intervention, they will fill out a brief questionnaire (i.e. "POL Activity Log Survey"). Post interaction with POL, POLs will go through a brief verbal consent process and ask community members to complete a brief anonymous 2-minute "Satisfaction Survey.", followed by basic demographic characteristics to understand the population they are reaching. For a clearer description of the process, see the study timeline in the next section. If the contact was not made face to face, the POL will ask the community member to complete the survey through an online anonymous survey.

Inclusion criteria for the community interaction is as follows:

• 18 or older

- Bilingual in English or Spanish
- The POL had a conversation with them or provided services to them as part of the CRISOL intervention.

We will use a shortened version of the consent form considering the information to be collected is not sensitive and consisting only of satisfaction items and demographics. Also, please, note that the surveys will not contain any contact information.

After completion of this survey, the POL will invite the community member to participate in a more in-depth 20-minute survey that will be managed by our staff. If the participant accepts, the POL will collect a phone/email so our staff can send the link for the survey. Additionally, participants will be invited to complete a follow-up survey 3 months after the first survey.

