#### Community contacts:

Post interaction with POLs, community members will complete a brief anonymous "Satisfaction Survey" based on their interaction with the POL, in addition to basic sociodemographic

characteristics. Community members will be provided with the informed consent script and must agree to participate before beginning the survey. The CRiSOL survey would be self-administered when the POLs and community contacts meet face-to-face, or administered by the POLs when interactions are made via phone or other media. The latter situation will be the case when social distancing measures are in place due to the coronavirus. The survey relies on Qualtrics®.

Note that by closing the survey, the answers of the individual cannot be accessed anymore except by the research team and no names or identifying information is included in the survey. A small incentive (i.e. a tote bag with the logo of the project) will be given to participants for their time when interactions are done face to face. This will not be possible when interactions are not face to face, such as during the coronavirus crisis.

For this second year, the study will be similar. Community members will complete an anonymous brief "satisfaction survey" after giving verbal consent (use of short consent version). Additionally, for this second year we are adding a new survey. POLs will invite community members to participate and collect phone numbers of the ones that agree. The research team will contact the community members that expressed interest, provide with a copy of the verbal consent and provide a link for them to take the survey. This survey will not collect any personal data. 300 community contacts will be invited to complete a follow-up survey 3 months after the completion of the first survey. The personal information needed to contact participants (i.e. phone number and first name) will be stored in a password-protected document.

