#### Community contacts:

As described above, after graduation, POLs will document their activity in the community using iPads furnished with an offline Qualtrics® survey. POLs will log every community contact they complete and indicate the date, time, and place of the contact ("POL Activity Log Survey"). For each community contact, POLs will document their community contacts' responses to the issues identified, which may include modeling of positive social norms, delivery of risk/harm reduction counseling, communication of health messages, linkage to resources, and navigation services to reduce SAVAME risk and impact. POLs will offer the community contact to take a satisfaction survey. The first survey ("Satisfaction Survey") can be self-administered by the community member and is designed to collect data on basic sociodemographic characteristics (e.g. age, gender, sexual orientation, race/ethnicity, etc.) and their satisfaction with the services received from the POL.

Collectively, we expect POLs will reach and register approximately 720 community contacts. These data will serve to establish the level of reach, implementation (feasibility), and maintenance of the intervention in the community and provide important community-level baseline data to describe the population reached by the POLs.

These quantitative data will be analyzed as follows: Parametric (one-way repeated measures ANOVA) or non-parametric tests (Friedman's test, general estimated equations), depending on

the level of measurement and observed distribution of the information. Analysis will be performed using IBM® SPSS® 22.0 and Stata 14.

All surveys offered as part of data collection on the community contact section of this protocol will be collected with and stored in Qualtrics®.

For the second year, we expect to follow same procedures as prior year. Additionally, we will be inviting community members to participate in an additional survey that measures risk behaviors and protective factors for SAVAME and COVID-19, as well as sociodemographic characteristics. After 3 months, those that expressed interest and gave consent will be contacted to complete a follow-up survey. These surveys will be collected and stored using Qualtrics ®.

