#### 19) Setting

Recruitment, interviews, and training sessions with POLs will take place at TPAC, located at [name].

Interactions between POLs and community contacts have no pre-determined setting, and will take place in settings that are most convenient for both the community contact and POL, and will be mutually decided by the community contact and POL. Due to COVID-19, these contacts might be held over the phone or online to minimize spread of disease. Efforts will be made to prioritize the community contact's setting preferences, including date and day of time. Recruitment with community contacts will take place at TPAC or a location that the respondent feels most comfortable and allows for privacy. The satisfaction survey will be delivered in this setting. POL's will be given training to ensure that locations chosen protect respondent's confidentiality and maximize respondent's comfort. Examples of locations are private meeting rooms at TPAC, private meeting rooms at Drexel University, etc.

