CRISOL Contigo: a Multi-level Intervention to Reduce the Disproportionate Toll of COVID-19 Among Latino Communities in Philadelphia. (CRISOL Contigo)

[name],
Professor of Community Health and Prevention, Drexel University

ClinicalTrials.gov Identifier: NCT04646616

Other Study ID Numbers: 3R21MD012352-02S1 (U.S. NIH Grant/Contract)

Date: October 28, 2020

Statistical Analysis Plan: CRISOL Contigo Aim 2. Outreach phase.

Summary:

A community popular opinion leader (POL) based intervention to promote measures to reduce COVID-19 risk, transmission, access to testing and treatment, reduction of the impact of COVID-19, and addressing the Substance Abuse, Violence, HIV/AIDS, and Mental health (SAVAME) syndemic in the community. POLs will interact within their networks counseling regarding COVID-19 and SAVAME factors. The POLs will refer individuals to appropriate community services. POLs will record basic sociodemographic characteristics of all community contacts, the issue addressed, and their response to it. The first 300 community contacts will be invited to complete a baseline and 3-month follow up surveys (via internet or phone). The content of the surveys includes: 1) COVID-19 related questions (knowledge, impact, symptoms, risk factors, access to testing and care, acceptability contact tracing, vaccine) 2) Biological risk factors, 3) Social determinants of health, 4) SAVAME outcomes and access to services.

Design: Quasi-experimental (pre-post), pragmatic, single arm, non-randomized, study.

Evaluation of this intervention will be guided by RE-AIM, a comprehensive evaluation framework to gauge a program's public health impact.

Below we outline the Statistical analysis plan of the individual-community contacts level.

The two co-primary outcomes will be:

- 1) Changes in risk of exposure to COVID-19, defined as the availability and/or usage of five modifiable risk factors: Use of mask, frequent hand washing, compliance with physical distance, avoidance of contact with high risk individuals. Combined (added) to create a score. [Time Frame: Baseline and 3 months]
- 2) Number of participants who lack access to health care [Time Frame: Baseline and 3 months]

Secondary outcomes include:

- 1) Number of participants with SAVAME-related factors [Time Frame: Baseline and 3 months]
- 2) Number of participants who lack access to health care [Time Frame: Baseline and 3 months]

Statistical analysis plan.

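### The protocol procedures and SAP describe no check that the phone or email used for the year-2 SAVAME/COVID-19 survey is private or safe to contact

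*Protocol*

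**What the plan says.** Protocol Section 5 (Community contacts) has the opinion leader (POL) invite the contact to a 20-minute survey managed by staff; if the person accepts, "the POL will collect a phone/email so our staff can send the link for the survey". Section 8 (Community contacts) mentions phone numbers only and says that staff will contact interested people, "provide with a copy of the verbal consent and provide a link for them to take the survey". A follow-up survey comes 3 months later.

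Section 10 (Community contacts) describes the instrument as "an additional survey that measures risk behaviors and protective factors for SAVAME and COVID-19". Section 3 expands the acronym as "Substance Abuse, Violence exposure, HIV/AIDS, and Mental Health (SAVAME". The SAP Summary lists "SAVAME outcomes and access to services" among the survey's contents and sets number, mode and timing: "The first 300 community contacts will be invited to complete a baseline and 3-month follow up surveys (via internet or phone".

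The nearest privacy step is in Section 19: "POL's will be given training to ensure that locations chosen protect respondent's confidentiality and maximize respondent's comfort". That section concerns where POLs meet and recruit contacts and where the satisfaction survey is given.

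**The concern.** The most sensitive instrument in the study is completed away from any setting that the study arranges, on a device or line it knows nothing about. A shared phone, a family email account or a call taken within earshot could show a partner or relative that the person is in the study, and possibly what it is about. Section 4 says that immigrant women experience more intimate partner violence and seek services less often. Section 15 accepts that contacts affected by violence or HIV may be vulnerable. The population is therefore one in which the protocol itself expects such harm to matter.

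There is also a data issue. The number of participants with SAVAME-related factors is a secondary outcome in the SAP, tested for change from baseline to 3 months in a single arm. People who cannot answer privately may not report violence, HIV risk or substance use. With no comparison group, a shift in disclosure between waves cannot be told apart from a real change.

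**Working it through.** **Step 1: do the existing safeguards reach this contact step?** The plan states no figure to reproduce, so this is a comparison of texts.

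| Safeguard | Where | What it covers | Reaches the year-2 survey contact? |
|---|---|---|---|
| Private location | Protocol 19 | POL meeting, recruitment, satisfaction survey | No |
| Private office | Protocol 13 | Qualitative interviews | No |
| Password protection, separate storage, identifiers | Protocol 8, 10, 13, 24, 25 | Data held by the study | No |
| Right to refuse, skip or withdraw | Protocol 13, 25 | Answering | Not once someone else has seen the message |
| Safety monitoring | Protocol 11 | Marked not applicable | No |

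Section 13 states that contacts face no potential risk because what they are asked is not sensitive. That fits the satisfaction and demographic items described just before it. It does not fit a survey on violence, HIV and substance use.

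**Step 2: how many contacts?** The SAP invites 300 people at two time points: 300 × 2 = 600 contact occasions at most, if everyone is reached at both. This is a ceiling on contacts, not a count of harms. The documents do not say how many devices are shared, how many participants live with someone from whom disclosure would be dangerous, or what the message says.

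**Step 3: when would poor privacy bias the pre-post result?** This is an illustration only, for one yes/no item such as violence exposure. My assumptions are: true status does not change; there are no false positives; reporting at the two waves is independent given true status; all 300 pairs are complete; and the test is a two-sided McNemar test at 0.05 (normal approximation). The SAP names paired t-tests and tests of proportions but states no alpha. Prevalence p and the disclosure probabilities s0 (baseline) and s1 (3 months) are assumed.

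- Reported at baseline only: b = p·s0·(1 − s1)
- Reported at 3 months only: c = p·(1 − s0)·s1
- Apparent change: c − b = p·(s1 − s0)
- Chance of a significant result ≈ Φ{[|c − b| − 1.96·√((b + c)/N)] / √((b + c − (c − b)²)/N)}

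*Equal disclosure.* With p = 20% and s0 = s1 = 70%, reported prevalence is 0.20 × 0.70 = 14% at both waves. Apparent change is zero and the false-positive rate stays at 5%. A real change would be shrunk to 70% of its size.

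*Unequal disclosure.* With p = 20%, s0 = 90%, s1 = 70%: b = 0.2 × 0.9 × 0.3 = 0.054; c = 0.2 × 0.1 × 0.7 = 0.014; change = −0.040. With N = 300, √(0.068/300) = 0.01506 and √(0.0664/300) = 0.01488, so (0.040 − 1.96 × 0.01506)/0.01488 = 0.705 and Φ(0.705) ≈ 76%.

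| Assumed true prevalence | 90% then 70%: apparent fall | Chance significant | 90% then 80%: apparent fall | Chance significant |
|---|---|---|---|---|
| 10% | 2.0 points | 47% | 1.0 point | 19% |
| 20% | 4.0 points | 76% | 2.0 points | 33% |
| 30% | 6.0 points | 91% | 3.0 points | 46% |

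If disclosure rises instead (70% then 90%), the sign reverses and the chances match the 90%-then-70% column. The SAP outcome pools several SAVAME factors without defining the rule, so a shift in one item would not pass through one-for-one.

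**The case against.** **The record is incomplete.** The consent pages were removed, and the questionnaire, contact form and message wording are not in the documents. A privacy prompt may exist there. This stands, and it limits the claim to what the protocol procedures and SAP describe. But a prompt inside the consent text or survey comes only after the message has arrived.

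**The message may be harmless.** Section 8 does not say that the consent text sits in the message body; it may already be behind the link. This stands. A reader might infer that every participant is sent a visible list of topics, and the text does not support that. Phone administration rests on the SAP alone, since the protocol describes a link.

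**Participants have some control.** They opt in after talking with someone from their own network, choose which number or email to give, can open a link when it suits them, and can skip questions. POLs are trained on vulnerability (Section 15). All of this lowers the risk; none of it is a check.

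**Contacts are not selected for violence.** A reader might infer that they are. Section 4 describes contacts as people who may be at risk for or affected by SAVAME conditions, but eligibility in Section 5 rests on age, language and having spoken with or been served by a POL. The SAP takes the first 300. So the documents do not show that those exposed are the people most at risk of violence.

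**The bias is conditional.** The described route is the same at both waves, and nothing in the documents shows that privacy would differ. This stands. The only opening is that the SAP allows two modes without fixing one per person.

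**Conclusion.** The gap is real: the written procedure sends study contact to a phone or email without asking whether it is private or safe, for a survey whose subjects include violence, HIV and substance abuse. The stated safeguards stop short of this step, and the risk section's description of contacts' information as not sensitive does not fit the instrument.

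The participant-safety side has a ceiling of 300 people and 600 contact occasions. How many would be harmed cannot be estimated. A reader might multiply the 600 by a guessed rate of partner violence, but the documents give no such rate, and the product would count messages rather than people.

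The statistical side is secondary. A reader might infer that the SAVAME change is biased as planned; the documents do not support that. Equal under-reporting at both waves gives no false change and only weakens a real one. A false change needs disclosure to differ between waves. Under the assumed drops of 10 to 20 percentage points the apparent fall is 1 to 6 points, with a 19% to 91% chance of significance, and every input to that range is an assumption. The case for changing the procedure rests mainly on safety and low cost.

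**What to change.** Add the following to the year-2 contact procedure in Protocol Sections 5 and 8:

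1. When the POL takes the contact detail, ask whether that phone or email is private to the person, and what message and times are safe. Record both for staff.
2. Send a neutral message that names no topics, with the consent text behind the link.
3. Open any phone administration by checking that the person can talk privately, and offer to reschedule.
4. Repeat the same steps at 3 months, including asking again whether the contact detail is still safe.

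Reword Section 13 so that the description of contacts' information as not sensitive applies to the satisfaction survey only, and state the risk for the year-2 survey separately.

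The cost is two questions on the contact form, one message template and one line in the phone script. Design, sample size and analysis are unchanged. The downside is a slightly lower contact rate where a participant gives no safe route or time.

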#### 6) Study Timelines

We anticipate that it will take approximately one month to enroll POLs for the CRiSOL training. During the enrollment period, POLs will complete baseline interviews that will take approximately 45 minutes. The CRiSOL training will consist of 40 hours, delivered in 4-hour training sessions at times that are convenient for the group of POLs and the research team. The initial training will be followed by 16 biweekly 3-hour reinforcement/booster sessions.

We anticipate that the CRiSOL intervention implementation will take place over a 8-month period. POLs will commit to complete and document interactions with at least 5 community contacts over each 2-week period. Each community contact will be asked to complete a brief two-minute anonymous "Satisfaction Survey" based on the interaction with the POL. We anticipate that it will take approximately four months to compile, clean, complete primary data analysis and prepare a manuscript and/or final report.

For the second year, we will invite the same POLs to participate. The COVID-19 training will consist of 16 hours, delivered in 4-hour training sessions at times that are convenient for the group of POLs and the research team. The training will be followed by 18 bi-monthly 2-hour booster sessions.

Please refer to the following study timeline:

FIRST Year timeline:

									N	1ont	:h							
		1	2	3	4	5	6	7	8	9	10	11	12	13	14	15	16	17
	IRB approval																	
POL Experience	POL Recruitment																	
	POL grand evaluation & overall training pre-test																	
	POL training modules, pre-test, post- tests																	
	POL overal training post-test																	
	POL montly booster training sessions																	
	POL outreach to community																	
	POL preliminar interview																	
	POL grand evaluation post-test																	
	POL exit interview																	
Community / Contact Experience	Community contact interact with POLs																	
	Community contacts take satisfaction survey																	
Facilitator Experience	Interview with Module Facilitators																	
	Data analysis, final report, manuscript																	

# SECOND Year – Extension

## Timeline

	Month												
	1	2	3	4	5	6	7	8	9	10	11	12	
IRB approval, intervention review and surveys programming													
POL re-training													
CRiSOL-COVID-19 intervention implementation													
POL monthly booster training sessions													
Baseline community contacts survey													
Follow up community contacts surveys													
POL exit interviews													
Follow up community contacts surveys													
CRISOL-COVID-19 intervention data cleaning, analysis and													
manuscript prep													
Community Resource/Service Assessment survey prep/IRB													
Community Resource/Service Assessment survey													
Community Resource/Service Assessment survey analyses,													
manuscript													
Data sharing, data dissemination													

## 7) Study Endpoints

The primary endpoint of this study is to be able to assess the feasibility, acceptability, and efficacy of a peer-driven intervention to address the factors that contribute to this syndemic, increase access to SAVAME and COVID-19 prevention and treatment services, and reduce the prevalence and impact of the syndemic conditions and COVID-19 on the Latino immigrant community in Philadelphia.

